2.3 Correlative Research

- 2.3.1 To assess the changes in immune infiltration (TISSUE: tumor-infiltrating lymphocytes – **TILs (CD-3, CD-8), PD-L1 and PD-1 expression**, pre- and post-Y90-RE and immunotherapy).
- 2.3.2 To analyze serial changes in **immune cells** (BLOOD) pre- and post-Y90-RE and immunotherapy
- 2.3.3 To determine changes in the expression profile and in levels of circulating tumor DNA (**ctDNA**) in blood pre- and post- treatment.
- 2.3.4 To evaluate **mutation burden** by whole-exome sequencing pre- and post-treatment (TISSUE)
- 2.3.5 To evaluate concomitant expression profile changes through **RNA-Seq** pre- and post-treatment (TISSUE)
- 2.3.6 To evaluate the **feasibility** of developing patient derived organoids, xenografts and/or cell-lines at the time of pre- and post-treatment biopsies
- 2.3.7 Correlation of outcomes based on **subtypes** of mCRC (sidedness, mutational/molecular subtypes)
- 2.3.8 To report on any *abscopal effects* seen in terms of responses outside the Y90-RE field.

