3.1 Inclusion Criteria

- 3.1.1 Age \geq 18 years
- 3.1.2 Histological or cytological confirmation of colorectal cancer with metastasis to the liver. Mismatch repair or microsatellite instability status of the tumor needs to be known. Tumors need to be mismatch repair proficient (for mismatch repair deficient tumors immunotherapy is already approved).
- 3.1.3 Patient must have at least 1 liver lesion measurable as defined in [Section 11.0](#).
- 3.1.4 Must have liver metastases and be appropriate for treatment with Y90-RE therapy as determined by the treating medical oncologist and interventional radiologist/oncologist, and nuclear medicine physician(s).

NOTE: the goal of therapy is safety and parenchymal sparing. Typically, since the treatment is personalized, the goal is to have at least 30% liver parenchymal sparing post treatment.

- 3.1.5 Must have a metastatic focus amendable to biopsy. It is permissible to use same or alternative lesion for biopsy for assessment for tumor response and changes in microenvironment (mandatory pre- and post-Y90-RE biopsy).
- 3.1.6 **At least 2 but no more than 3 lines of therapy** allowed in metastatic setting. These include at least treatment with a fluoropyrimidine, oxaliplatin, and/or irinotecan-based

therapy and an anti-EGFR therapy if RAS wild-type (unless deemed intolerant or not suitable by the treating oncologist), with or without an anti-VEGF therapy.

NOTE: adjuvant and/or maintenance chemotherapy does not count as an additional line of therapy. (Patients with more than 3 lines of therapy are at risk for liver disease from prior systemic therapies and would not be reasonable candidates for Y90-RE).

- 3.1.7 At least a 4-week gap between anti-VEGF therapy and the IR Tc-99m labelled MAA eligibility mapping
- 3.1.8 ECOG Performance Status (PS) 0 or 1 ([Appendix I](#)).
- 3.1.9 Negative *serum* pregnancy test done ≤ 7 days prior to registration, for persons of childbearing potential only.

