7. Gross (dipstick) urine examination: Leukocytes, nitrite, pH, protein, glucose, ketone, urobilinogen, bilirubin, blood (hemoglobin and erythrocytes). If abnormalities are detected by dipstick, then a microscopic sediment test should also be performed. If a UTI is suspected, it can be treated.
8. Durvalumab administration over 60 minutes. Following infusion, subjects must be observed for 30 minutes post infusion for potential infusion related reactions. The number of doses administered is per dose level for each patient cohort.
9. The 2nd durvalumab dose can be done \leq 5 days prior to Y90-RE or same day as long as it is before the Y90-RE.
10. Blood biomarkers will be collected in the morning of visit. Kits are required.
11. Tissue specimens must be collected the following timepoints: pre-treatment [screening/prior to cycle 1 of Durvalumab (fresh as well as archived if available)], and post-treatment. Kits are required (banking, clinical as well as real-time send out).
12. Visit will occur 8 weeks after Y90-RE.
13. Clinical follow-up visits will be performed at least every 3 months (or as per standard physician practice) for 2 years.
14. Cohort 1- Durvalumab given at cycle 1 and cycle 2 only
15. Cohort 2- Durvalumab given at cycle 1, 2, and 4
16. Dose escalation cohort- Durvalumab given cycle 1, 2, 4 and 5
17. Dose expansion cohort- Durvalumab given cycle 1, 2, 3, 4, and 5
18. As long as the lesion is amenable to a biopsy and is done, the biopsy can be done on the Tc-99m labelled MAA eligibility mapping day to save patient a visit. Has to be prior to anti-PD1 therapy though. From a safety perspective since we need to know about the shunting to other organs prior to the Y90-RE, the mapping can be done during the screening or even prior to considerations for this study if already performed within 12 months of intended Y90-RE, it would not need to be repeated unless as per interventional radiology. Biopsy still needs to be done as noted.
19. If there is complete response of the lesion in the field of Y90-RE, tissue biopsy of the field would still be done to assess for the immune changes and an alternative tumor lesion can be biopsied for testing of the tumor itself.
20. At the time of progression, patient would be approached for a tissue biopsy and research blood sampling similar to the end of treatment visit.

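### The mandatory pre- and post-treatment biopsies may come from different metastases, inside or outside the Y90-RE field, and the plan does not separate the resulting tissue pairs

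*Combined protocol and SAP*

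**What the plan says.** Criterion 3.1.5 sets the site requirement as "Must have a metastatic focus amendable to biopsy", which limits the biopsy neither to the liver nor to the treated field. On the choice of lesion for the two mandatory samples it says: "It is permissible to use same or alternative lesion for biopsy for assessment for tumor response and changes in microenvironment".

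The test schedule (section 4.1) adds two relevant footnotes. Footnote 11 gives the timing as "pre-treatment [screening/prior to cycle 1 of Durvalumab (fresh as well as archived if available)], and post-treatment", without naming a lesion. Footnote 19 covers complete response of a lesion in the Y90-RE field: "tissue biopsy of the field would still be done to assess for the immune changes and an alternative tumor lesion can be biopsied", the second part being for tumor testing.

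The tissue goals are before-and-after comparisons. Goal 2.3.1 begins "To assess the changes in immune infiltration" and covers TILs, PD-L1 and PD-1; 2.3.4 covers mutation burden by exome sequencing and 2.3.5 covers RNA-Seq. Section 1.3.1 compares tumor-infiltrating cells at two tissue time points. Section 17.3 defines the paired change as the post-treatment value minus the pre-treatment value within patient, with no reference to lesion or field.

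Untreated disease is expected. The note to 3.1.4 states that "the goal is to have at least 30% liver parenchymal sparing post treatment", and goal 2.3.8 is "To report on any *abscopal effects* seen in terms of responses outside the Y90-RE field".

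**The concern.** A within-patient tissue comparison isolates treatment change only if the two samples differ in timing alone. Under 3.1.5 they may also differ in lesion, and the post-treatment sample may lie outside the field that received Y90-RE. Two metastases in one patient can differ in clones, mutation burden or infiltrate without any treatment effect. A post-treatment sample from outside the field carries the systemic effect of durvalumab and any abscopal effect, but not the local radiation effect that sections 1.1 and 1.2.4 put at the center of the rationale.

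Elsewhere the protocol keeps the two compartments apart: liver-PFS is restricted to lesions in the field (2.2.5), and duration of response is to be determined in and outside it (2.2.8). The biopsies have no such separation. Section 1.4.6 bases the maximum of 18 partly on the paired biopsies. The expansion cohort's stated main objective is immune-cell change (17.3), which section 1.3.1 measures in blood or tumor. The results are meant to inform a Phase II trial. If lesion and field status are not recorded at the time, they may not be recoverable later.

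**Working it through.** **The plan's own figure.** Section 17.3 gives a 95% confidence interval half-width of 0.5 SD for the mean paired difference with 18 patients. Half-width = t(0.975, n−1)/√n = 2.110/4.243 = 0.497 SD. The figure reproduces. Its unit is whatever SD the paired difference turns out to have, so mixing lesions does not falsify it. Mixing can enlarge that SD and change what the mean estimates.

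**Inputs.** From 17.3: n = 18 and a 25% change taken as biologically meaningful. The documents do not give the share of cross-lesion pairs (q), the between-lesion share of within-patient biopsy variance (ρ), the share of post-treatment biopsies outside the field (q_out), or the ratio of out-of-field to in-field change (k). These are assumed and shown as ranges. The shares q and q_out are distinct: a cross-lesion pair can lie wholly in the field, and a same-lesion pair wholly outside it.

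**Effect on the mean.** Observed mean = D × [1 − q_out × (1 − k)], with D = 25%:

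| q_out | k = 0 | k = 0.5 |
|---|---|---|
| 1/6 | 20.8% | 22.9% |
| 1/3 | 16.7% | 20.8% |
| 1/2 | 12.5% | 18.8% |

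**Effect on precision.** Let s² be the sampling variance within a lesion and τ² the variance between lesions. A same-lesion difference has variance 2s²; a cross-lesion difference has 2s² + 2τ². With ρ = τ²/(s² + τ²), the variance ratio averaged over pairs is 1 + q × ρ/(1 − ρ). At ρ = 0.5 (τ = s) and q = 1/3 it is 1 + 1/3 = 1.333; the SD ratio is 1.155 and the half-width is 0.497 × 1.155 = 0.574. At q = 1 the ratio is 2, the SD ratio 1.414 and the half-width 0.703. Half-widths at n = 18, in same-lesion SD units:

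| ρ | q = 1/3 | q = 1 |
|---|---|---|
| 0.2 | 0.518 | 0.556 |
| 0.5 | 0.574 | 0.703 |
| 0.7 | 0.663 | 0.908 |

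This model leaves out patient-to-patient variation in the true change. Including it would make the relative widening smaller.

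**Footnote 19.** Its two clauses act differently. The immune readout after an in-field complete response stays in the field. Only tumor testing may move to another lesion. A switch driven by outcome can therefore arise from this footnote for tumor testing such as sequencing (2.3.4, and probably 2.3.5), but not for 2.3.1.

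**The case against.** Several points on the other side stand.

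- A reader might infer that the best responders are systematically biopsied outside the field. Footnote 19 does not support that for the immune endpoints, because the field is still biopsied. For sequencing the move is permitted, not required, and the alternative may be no usable tumor sample.
- A reader might picture one irradiated and one unirradiated sample in a pair. No lesion has received Y90-RE at the pre-treatment biopsy; the contrast is between lesions inside and outside the planned field.
- Out-of-field tissue is informative. Section 1.1 names the abscopal effect, goal 2.3.8 studies it, and durvalumab acts systemically. Such samples should be labelled and shown apart, not discarded.
- The tissue goals are correlative. Section 17.3 plans no formal hypothesis test, and 17.5 treats laboratory correlates as exploratory.
- Flexibility serves feasibility: under 3.1.15 a patient whose tissue is inaccessible cannot take part.
- Collection details are deferred to a companion laboratory manual that is not among the documents, and it may record the biopsy site. Any lesion rule there would need to agree with 3.1.5.

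None of this removes the general permission in 3.1.5, which leaves both the immune and the sequencing comparisons open to mixed pairs.

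**Conclusion.** The concern holds for the paired tissue endpoints: TILs, PD-L1/PD-1, tumor flow cytometry, exome and RNA-Seq. As written, the plan allows treatment effect to be mixed with between-lesion difference and field status, and nothing supplied would separate them. Blood immune cells, ctDNA and the safety and MTD goals are untouched, and the 0.5 SD statement in 17.3 is arithmetically right.

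The size rests on assumption. With q_out from 1/6 to 1/2 and k from 0 to 0.5, a true 25% in-field change averages about 12.5% to 23%. With equal between-lesion and sampling variance, the interval is about 15% wider if one third of pairs are cross-lesion. A reader might take 41% as the general figure, but it applies only if every pair is cross-lesion. Likewise, zero change outside the field is the extreme case and runs against the trial's own abscopal hypothesis. This is a worthwhile, inexpensive correction to exploratory endpoints; it does not threaten the trial's main conclusion.

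**What to change.** 1. Amend 3.1.5 so that, where safe and feasible, both biopsies come from the same lesion inside the planned Y90-RE field, with an alternative lesion still allowed otherwise. Footnote 18 allows the pre-treatment biopsy on the mapping day, when field information may be at hand.
2. Record lesion identity and in-field or out-of-field status for every biopsy, consistent with the laboratory manual.
3. For the immune tissue endpoints, present same-lesion in-field pairs as the main summary. Show different-lesion and out-of-field pairs separately; the out-of-field pairs also inform 2.3.8.
4. For exome and RNA-Seq, report all pairs by lesion and field status, and state how many in-field complete responders lack a same-lesion tumor sample. Restricting this analysis to same-lesion in-field pairs could drop those responders and create an outcome-linked selection of its own.

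The cost is protocol wording, two data fields and fewer pairs in the main tissue summary. The half-width rises from 0.497 SD at n = 18 to 2.201/√12 = 0.635 SD at n = 12 and 2.306/√9 = 0.769 SD at n = 9. With a third of pairs set aside, 0.635 is wider than the 0.574 obtained by pooling at ρ = 0.5 and q = 1/3, so the gain is a clear meaning, not necessarily a narrower interval. No extra biopsy is needed.

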3.2 Exclusion Criteria

- 3.2.1 Any of the following laboratory abnormalities:
 - Hemoglobin <9.0 g/dL
 - Absolute neutrophil count (ANC) $<1500/\text{mm}^3$
 - Platelet count $<100,000/\text{mm}^3$
 - Total bilirubin $>1.5 \times \text{ULN}$ or $>2.0 \text{ mg/dL}$, whichever is lowest (exception for patients with Gilbert Syndrome, who cannot have a total bilirubin $> 3.0 \text{ mg/dL}$)
 - Alanine aminotransferase (ALT) and Aspartate transaminase (AST) $>2.5 \times \text{ULN}$
 - Serum creatinine $> 1.5 \times \text{ULN}$ or 2.0 mg/dL , whichever is lowest.

OR

 - Calculated creatinine clearance $<30 \text{ ml/min}$ using the Cockcroft-Gault formula below:

Cockcroft-Gault Equation:

$$\text{Creatinine clearance for males} = \frac{(140 - \text{age}) (\text{weight in kg})}{(72) (\text{serum creatinine in mg/dL})}$$

$$\text{Creatinine clearance for females} = \frac{(140 - \text{age}) (\text{weight in kg}) (0.85)}{(72) (\text{serum creatinine in mg/dL})}$$

**NOTE: These can be repeated if outside of range to determine eligibility. Growth factor support not allowed. Transfusion support for low hemoglobin allowed up to 5 days prior to start of treatment.*

3.2.2 Patients with any of the following contraindications to TheraSphere treatment:

- Shunting to the bowel along the gastrointestinal tract
- Lung shunting of $\geq 15\%$
- Estimated dose to lungs ≥ 30 Gy in a single administration
- Cumulative estimated dose to lungs ≥ 50 Gy for multiple administrations
- Liver size ≤ 1.5 L

3.2.3 Prior radiation therapy unless reviewed by the IDE sponsor and approved. This is on a case-by-case basis. Radiation plans should be provided for review.

3.2.4 Persons who are actively breastfeeding a child and unwilling to discontinue.

3.2.5 Co-morbid systemic illnesses, **infections**, or other severe concurrent disease which, in the judgment of the investigator, would make the patient inappropriate for entry into this study or interfere significantly with the proper assessment of safety and toxicity of the prescribed regimens.

3.2.6 Untreated central nervous system (CNS) metastatic disease (including spinal cord and leptomeningeal disease). **NOTE:** Patients with previously treated CNS metastases that are radiographically and neurologically stable for ≥ 6 weeks are permitted.

3.2.7 Uncontrolled intercurrent illness including, but not limited to, autoimmune disease, ongoing or active infection, or psychiatric illness/social situations that would limit compliance with study requirements. Please note: with respect to autoimmune disease, patients with history of **severe** autoimmune disease or **active** autoimmune disease within two years of study entry or have a medical condition that requires systemic immunosuppression are excluded from the study.

3.2.8 Received any other investigational agent incorporating chemotherapy and/or biologics within 14 days prior to first dose of durvalumab which would be considered as a treatment for the primary neoplasm. For patients on active treatment, last treatment and 1st dose of Durvalumab should be at least ≥ 14 days. **EXCEPTION:** Other forms of concurrent observational studies are permitted.

3.2.9 Other active malignancy ≤ 3 years prior to registration. **EXCEPTIONS:** Non-melanoma skin cancer, lentigo maligna- in-situ, or carcinoma-in-situ of the cervix. Also, prior malignancy already treated with curative intent and with no known active disease present would be considered eligible.

3.2.10 History of unstable cardiac disease defined as one of the following:

- Congestive heart failure $>$ class II New York Heart Association (NYHA). ([Appendix II](#))
- Unstable angina (angina symptoms at rest) or new onset angina (began ≤ 3 months prior to registration)
- Myocardial infarction ≤ 3 months
- Uncontrolled cardiac ventricular arrhythmias. **EXCEPTION:** Subjects that are stable on anti-arrhythmic therapy are eligible.

- 3.2.11 Any concurrent chemotherapy, biologic, or hormonal therapy for cancer treatment within 14 days of first dose of durvalumab. **NOTE:** Subjects can be screened during washout period.
- 3.2.12 History of severe allergic reactions (i.e. Grade 4 allergy, anaphylactic reaction from which the subject did not recover \leq 6 hours of initiation of supportive care)
- 3.2.13 Failure to recover from toxicities from prior anti-cancer therapy, defined as having not resolved to National Cancer Institute (NCI) CTCAE version 5.0 Grade \leq 1.
EXCEPTIONS: Alopecia and laboratory values listed per the exclusion criteria. Also subjects with irreversible toxicity that is not reasonably expected to be exacerbated by any investigational products (i.e. hearing loss) will be permitted.
- 3.2.14 Use of steroids. **EXCEPTIONS:** Systemic glucocorticoids will be permitted as long as it is \leq 10 mg of prednisone equivalent. Topical steroids, such as bronchodilators and local steroid injections are also permitted if clinically required.
- 3.2.15 Patients with renal failure currently requiring dialysis of any kind.
- 3.2.16 Patients weighing <30 kg will be excluded from enrollment
- 3.2.17 History of allogenic organ transplantation

4.0 Test Schedule

4.1 Test schedule for metastatic CRC

Tests and procedures	Screening		Active Monitoring Phase					
	Reg	Cycle 1	Cycle 2 (2 nd dose of Durva + Y90-RE)*	Cycle 3	Cycle 4	Cycle 5	End of treatment visit ¹²	Clinical Follow-up ¹³ (every 3 months)
Window	21 days	±5 days	±5 days	±5 days	±5 days	±5 days	±5 days	
History and exam ³ , Wt ⁵ , BP, HR, ECOG PS	X							
Exam, Wt ⁵ , BP, HR, ECOG PS		X	X	X	X	X	X	X
Adverse event assessment	X	X	X	X	X	X	X	X
Concomitant medication review	X	X	X	X	X	X	X	X
Height	X							
IR Consult	X							
Pregnancy test ¹	X		X		X		X	X
Hematology group CBC w/ 5-part differential	X	X	X	X	X	X	X	X
Chemistries ²¹	X	X	X	X	X	X	X	X
Thyroid Function Test TSH, free T4, amylase, lipase, Vitamin D	X		X		X		X	X
Creatinine clearance	X	X	X	X	X	X	X	X
Coagulation PT, PTT, INR	X						X	
Cholesterol, triglycerides	X							
IR Tc-99m labelled MAA eligibility mapping		X ¹⁸						
Tumor measurement ²	X						X	X
ECG ⁶	X		X		X		X	
Urinalysis ⁷	X	X	X	X	X	X	X	X
Administer durvalumab ^{8,R}		X ^{16,17,18,19}	X ^{9,16,17,18,19}	X ¹⁹	X ^{17,18,19}	X ^{17,18,19}		
Administer Y90-RE			X					
Patient Questionnaire Booklets ⁴ (Appendix III)		X	X	X	X	X	X	
Mandatory Research Specimens (see companion Lab Manual) ^{10,R}	X	X ^{14,15,16,17}	X ^{14,15,16,17}	X ¹⁷	X ^{15,16,17}	X ^{15,16,17}	X	
Mandatory Research Tissue specimens (see companion Lab Manual) 11,R	X (Pre- treatment) ₁₈						X (Post- treatment) _{19, 20}	

Cycle = 14 days

1. For women of childbearing potential only. Serum pregnancy test. Must be done \leq 7 days prior to registration.
2. A scan is required at baseline prior to the first dose of durvalumab. The scan does not need to be repeated as long as it is \leq 28 days prior to registration. Preferably we would recommend a CT of the chest and pelvis; and an MRI of the abdomen for assessment of liver metastases. If an MRI cannot be performed, a CT chest, abdomen, and pelvis would be acceptable. Please use same imaging throughout the study.
3. History and exam include prior surgery, cancer-related and other treatment and known positivity for Hepatitis B surface antigen, Hepatitis C virus antibodies, and Human Immunodeficiency Virus antibodies 1 /-2.
4. Patient questionnaire booklets **must** be used; copies are not acceptable for this submission
5. Body weight to be measured within 72 hours prior to durvalumab administration.
6. Single 12-lead ECG after 5 min rest in supine position.
7. Gross (dipstick) urine examination: Leukocytes, nitrite, pH, protein, glucose, ketone, urobilinogen, bilirubin, blood (hemoglobin and erythrocytes). If abnormalities are detected by dipstick, then a microscopic sediment test should also be performed. If a UTI is suspected, it can be treated.
8. Durvalumab administration over 60 minutes. Following infusion, subjects must be observed for 30 minutes post infusion for potential infusion related reactions. The number of doses administered is per dose level for each patient cohort.
9. The 2nd durvalumab dose can be done \leq 5 days prior to Y90-RE or same day as long as it is before the Y90-RE.
10. Blood biomarkers will be collected in the morning of visit. Kits are required.
11. Tissue specimens must be collected the following timepoints: pre-treatment [screening/prior to cycle 1 of Durvalumab (fresh as well as archived if available)], and post-treatment. Kits are required (banking, clinical as well as real-time send out).
12. Visit will occur 8 weeks after Y90-RE.
13. Clinical follow-up visits will be performed at least every 3 months (or as per standard physician practice) for 2 years.
14. Cohort 1- Durvalumab given at cycle 1 and cycle 2 only
15. Cohort 2- Durvalumab given at cycle 1, 2, and 4
16. Dose escalation cohort- Durvalumab given cycle 1, 2, 4 and 5
17. Dose expansion cohort- Durvalumab given cycle 1, 2, 3, 4, and 5
18. As long as the lesion is amenable to a biopsy and is done, the biopsy can be done on the Tc-99m labelled MAA eligibility mapping day to save patient a visit. Has to be prior to anti-PD1 therapy though. From a safety perspective since we need to know about the shunting to other organs prior to the Y90-RE, the mapping can be done during the screening or even prior to considerations for this study if already performed within 12 months of intended Y90-RE, it would not need to be repeated unless as per interventional radiology. Biopsy still needs to be done as noted.
19. If there is complete response of the lesion in the field of Y90-RE, tissue biopsy of the field would still be done to assess for the immune changes and an alternative tumor lesion can be biopsied for testing of the tumor itself.
20. At the time of progression, patient would be approached for a tissue biopsy and research blood sampling similar to the end of treatment visit.
21. Creatinine, ALP, ALT, AST, total bili, direct bilirubin, AlkPhos, GGT, total protein, uric acid, BUN, Na, K, Ca, Cl, LDH, CPK, inorganic phosphate, CEA, CA-19-9, ESR, CRP

* 2 research blood drawn (pre-post Y90 RE on the day of procedure). Timing not important.

R Research funded (see Section 19.0)

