6.0 Enrollment Procedures

- 6.1 Call the GI clinical research coordinator/PI for slot reservation.
- 6.2 Correlative research is mandatory in this trial and the subject will automatically be registered to this component (see Sections 3.19d, 3.19e 14.0, 17.31, 17.32, and 17.34). Please contact PI if there are any questions or concerns or exceptions.
- 6.3 Documentation of IRB approval must be on file before an investigator may enroll any patients.
- 6.4 Prior to enrollment, verify the following:
 - IRB approval
 - Patient eligibility
 - Existence of a signed consent form
 - Existence of a signed authorization for use and disclosure of protected health information
- 6.5 Treatment cannot begin prior to screening and must begin \leq 21 days after screening.
- 6.6 Pretreatment tests/procedures (see Section 4.0) must be completed within the guidelines specified on the test schedule.
- 6.7 All required baseline symptoms (see Section 10.3) must be documented and graded.
- 6.8 Treatment on this protocol must commence at University of Iowa Holden Comprehensive Cancer Center institution under the supervision of a medical oncologist.
- 6.9 Case has been discussed or an interventional oncologist has seen the patient and confirms the patient is a suitable candidate for this study.
- 6.10 Study drug is available on site.
- 6.11 Blood draw kit is available on site.

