11.2 Definitions of measurable and non-measurable disease

11.21 Target Lesion Response mRECIST

- **Complete Response** - Disappearance of any intratumoral arterial enhancement in all target lesions.
- **Partial Response** - At least a 30% decrease in the sum of the diameters of viable (enhancement in the arterial phase) target lesions, taking as reference the baseline sum of the diameters of target lesions.
- **Progressive Disease** – An increase of at least 20% in the sum of the diameters of viable (enhancing) target lesions, taking as reference the smallest sum of the diameters of viable (enhancing) target lesions recorded since treatment started.
- **Stable Disease** – Any cases that do not qualify for either partial response or progressive disease.

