17.5.3 Overall Response Rate

Overall response rate is defined as the proportion of evaluable patients that have achieved a complete response or partial response using mRECIST evaluation criteria. ORR will be evaluated at 2 months post-Y90RE treatment (\pm 5 business days).

ORR will be analyzed descriptively as a point estimate with a 95% confidence interval.

Results will be reported consistent with RECIST v1.1 (Appendix A.9).

An “evaluable subject” for the purpose of evaluation of the combinatorial therapy is one who receives both Y90-radioembolization and at least 1 dose of durvalumab.

Subjects who do not receive Y90-RE or received only a single incomplete dose of immunotherapy (i.e., allergic reaction), are considered non-evaluable for assessment of efficacy. These subjects would be replaced for the proposed sample size of 18.

All subjects included in the study must be assessed for response to treatment, even if there are major protocol treatment deviations or if they are ineligible.

Each subject will be assigned one of the following categories: 1) complete response (mRECIST), 2) partial response (mRECIST), 3) stable disease (mRECIST), 4) progressive disease (mRECIST), 5) early death from malignant disease, 6) early death from toxicity, 7) early death because of other cause, or 9) unknown (not assessable, insufficient data).

Category 4 (protocol specific definition): includes clinical progression as determined by the principal investigator and confirmed by the independent data and safety monitoring committee (DSMC).

Category 5 (protocol specific definition): death from malignant disease as determined by the principal investigator and confirmed by the independent data and safety monitoring committee (DSMC).

Category 6 (protocol specific definition): death from toxicity as determined by the principal investigator and confirmed by the independent data and safety monitoring committee (DSMC).

Category 7 (protocol specific definition): includes death not meeting categories 5 or 6, or death defined as not otherwise specified.

Category 9 (protocol specific definition): includes subjects who did not receive radioembolization, or who did not receive at least 1 complete infusion of durvalumab, or who did not undergo follow-up imaging (other than for clinical progression, toxicity, or death), or subjects who are lost to follow-up.

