- All measurements should be taken and recorded in metric notation, using a ruler or calipers. All baseline evaluations should be performed as closely as possible to the beginning of treatment and never more than 4 weeks before the beginning of the treatment.
- The same method of assessment and the same technique should be used to characterize each identified and reported lesion at baseline and during follow-up.
- Clinical lesions will only be considered measurable when they are superficial (e.g., skin nodules and palpable lymph nodes). For the case of skin lesions, documentation by color photography, including a ruler to estimate the size of the lesion, is recommended.

A.2 Methods of Measurement

- CT and MRI are the best currently available and reproducible methods to measure target lesions selected for response assessment. Conventional CT and MRI should be performed with cuts of 10 mm or less in slice thickness contiguously. Spiral CT should be performed using a 5 mm contiguous reconstruction algorithm. This applies to tumors of the chest, abdomen and pelvis. Head and neck tumors and those of extremities usually require specific protocols.
- Lesions on chest X-ray are acceptable as measurable lesions when they are clearly defined and surrounded by aerated lung. However, CT is preferable.
- When the primary endpoint of the study is objective response evaluation, ultrasound (US) should not be used to measure tumor lesions. It is, however, a possible alternative to clinical measurements of superficial palpable lymph nodes, subcutaneous lesions and thyroid nodules. US might also be useful to confirm the complete disappearance of superficial lesions usually assessed by clinical examination.
- The utilization of endoscopy and laparoscopy for objective tumor evaluation has not yet been fully and widely validated. Their uses in this specific context require sophisticated equipment and a high level of expertise that may only be available in some centers. Therefore, the utilization of such techniques for objective tumor response should be restricted to validation purposes in specialized centers. However, such techniques can be useful in confirming complete pathological response when biopsies are obtained.

- Tumor markers alone cannot be used to assess response. If markers are initially above the upper normal limit, they must normalize for a patient to be considered in complete clinical response when all lesions have disappeared.

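### The 28-day limit on the baseline scan runs from registration, so a permitted scan can be more than 4 weeks old at first dose, against Appendix IV.A, A.1

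*Combined protocol and SAP*

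**What the plan says.** Three places bear on the age of the baseline scan, and they use three different anchor dates.

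- **Section 4.1, footnote 2 (registration).** "A scan is required at baseline prior to the first dose of durvalumab", and "The scan does not need to be repeated as long as it is" at most "28 days prior to registration".
- **Section 6.5 (screening).** "Treatment cannot begin prior to screening and must begin" no later than "21 days after screening". The Screening/Reg column of the test schedule carries the same 21-day window.
- **Appendix IV.A, A.1 (start of treatment).** Baseline evaluations are to be as near the start of treatment as possible, and "never more than 4 weeks before the beginning of the treatment".

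Section 6.6 tells staff to complete pretreatment tests as the test schedule specifies, so footnote 2 is the rule they will apply. No section asks for a repeat scan when the first dose falls more than 28 days after the scan. The note to section 2.2 sets the landmark for the secondary endpoints at the initiation of immunotherapy.

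**The concern.** A site can follow footnote 2 exactly and still break the only limit in the protocol that is tied to the start of treatment.

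Partial response is defined by "taking as reference the baseline sum of the diameters of target lesions" (section 11.21). Progression is referenced to the smallest sum since treatment started. Section 11.1 schedules no scan between baseline and the end-of-treatment visit, so at that first assessment the baseline is in practice the reference for progression too. A lesion that appeared between an old scan and first dose would also count as new. ORR and DCR are both read at about this visit, 2 months after Y90-RE. Whatever the tumour did between the scan and the first dose is therefore attributed to the study treatment, by an amount that depends on each patient's scan date.

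**Working it through.** **Inputs.** Scan to registration: at most 28 days (footnote 2). Screening to treatment: at most 21 days (section 6.5). Limit before treatment: 4 weeks (A.1). Last prior therapy to first dose: at least 14 days (sections 1.4.6 and 3.2.8). Sample size: 18.

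**The plan's own figure.** 4 × 7 = 28 days. Let g be the days from registration to first dose. The oldest permitted scan at first dose is 28 + g days. This equals 28 only if g = 0, that is, if the patient is dosed on the day of registration.

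**How large g can be.** Let d be the days from screening to registration. Section 6.5 gives g ≤ 21 − d, so the maximum scan age is 28 + (21 − d) = 49 − d.

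| Screening to registration (d) | Largest g | Oldest permitted scan at first dose | Excess over 28 |
|---|---|---|---|
| 0 | 21 | 49 | 21 |
| 7 | 14 | 42 | 14 |
| 14 | 7 | 35 | 7 |
| 20 | 1 | 29 | 1 |
| 21 | 0 | 28 | 0 |

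**Prior therapy inside the interval.** With a 49-day-old scan, prior therapy can continue for 49 − 14 = 35 days after the scan. With a 28-day-old scan the figure is 28 − 14 = 14 days.

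**Worst-case illustration of size.** The documents give no growth rate. Assume that tumour volume doubles in 50 to 150 days with no treatment effect. Over the 21 excess days, diameter grows by a factor 2^(21/(3 × doubling time)):

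- 50 days: 2^(21/150) = 1.102
- 150 days: 2^(21/450) = 1.033

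To show a 30% decrease from the scan, the true shrinkage after first dose must then be 1 − 0.70/1.102 = 36%, or 1 − 0.70/1.033 = 32%.

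If prior therapy instead shrank diameters by 10% or 3% over the same days (an assumed mirror image), the shrinkage needed would fall to 1 − 0.70/0.90 = 22%, or 1 − 0.70/0.97 = 28%. These figures apply only to a patient at the limit of both windows. They use whole-tumour diameter, whereas mRECIST measures the enhancing part.

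**Effect on a rate.** One reclassified patient in 18 moves ORR or DCR by 1/18 = 5.6 percentage points.

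**The case against.** **The 21 days run from screening, not registration.** This stands. If registration closes screening just before dosing, the maximum is close to 28 days. A scan taken during the 21-day screening window is at most 21 days old at first dose, so only a scan carried in from before screening can be too old. But footnote 2 expressly allows such scans, and the shared Screening/Reg column does not separate the two dates.

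**A.1 belongs to a RECIST quick reference, while response is by mRECIST and iRECIST.** This stands in part. Section 17.5.3 invokes the appendix only for reporting: "Results will be reported consistent with RECIST v1.1 (Appendix A.9". A.1 is nonetheless protocol text. Neither section 11 nor the mRECIST and iRECIST material gives any other baseline window.

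**Little depends on it.** The primary goal is feasibility and safety, and ORR and DCR are descriptive. With an illustrative 5 responders in 18, the exact 95% interval is 10% to 53%, wide beside a shift of 2 to 6 points in the shrinkage that some patients need. This limits the severity, but the contradiction remains.

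**Stronger readings that a reader might infer.**

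- *Old scans bias ORR and DCR downward.* This considers only untreated growth. Section 1.4.6 lets patients interrupt current chemotherapy to join, so shrinkage from prior therapy can be credited to the study regimen.
- *Every response category is a change from this scan.* Complete response is loss of arterial enhancement, and after the first on-study scan the baseline need not be the reference for progression.
- *The count should run on to embolization.* The two weeks from first durvalumab to Y90-RE are by design (section 7.1.2). A scan meeting A.1 could be 28 + 14 = 42 days old by then.
- *The +5-day Cycle 1 window adds to the 49 days.* Nothing says that the visit window extends section 6.5.

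**Conclusion.** The inconsistency holds. Footnote 2 permits a baseline scan more than 28 days old at first durvalumab dose, which A.1 rules out. The permitted maximum is 49 days if screening and registration coincide, and 49 − d days if registration comes d days after screening. This is what the text allows, and the documents do not show how many patients would be affected.

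The consequence is possible misclassification, in either direction, of partial response, stable disease and first-assessment progression in two descriptive secondary endpoints. The 36% to 32% figures are a worst case that rests on assumed doubling times and are not an estimate of bias in the trial's ORR. The point is modest, but the change is worth making because it is cheap and asks for nothing that A.1 does not already require.

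**What to change.** Reword footnote 2 so that the baseline scan is no more than 28 days before the first durvalumab dose, and add that it is repeated if the start is delayed beyond that. This matches A.1 and the landmark in section 2.2. A patient dosed 21 days after registration would then need a scan no more than 28 − 21 = 7 days before registration, or a repeat.

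At dose levels −1 and −2 the tables place durvalumab only after Y90-RE. Wording the anchor as the first study treatment, which is the first durvalumab dose at levels 1 to 4, would cover those levels as well.

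The cost is a wording change and an occasional repeat scan. The change shortens the interval in which earlier therapy can affect the reference but does not remove it, since up to 14 days of prior therapy can still follow a 28-day-old scan. Recording the scan date and the last prior treatment date would let the report show that interval for each patient.
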